## 10.2. Secondary endpoints

**1) Kinetics of megakaryocyte recovery:** Parameters to be assessed will include median time to reach platelet count  $\geq 50,000/\mu\text{L}$  and  $\geq 100,000/\mu\text{L}$ , number of days of platelet transfusion, rates of platelet transfusion-independence, median time to reach platelet transfusion-independence and rates of CSBE. The initial time point for assessing different platelet recovery periods will be the first day of remission IC. The number of days of platelet transfusion will be defined as the total number of days in the cycle, beginning with the first day of study drug administration, in which a patient received transfusion. The time to transfusion-independent platelet recovery will be defined as the number of days from the first day of IC until the first of the 5 consecutive days with platelet count equal to or greater than  $50,000/\mu\text{L}$  without a platelet transfusion. For patients who do not achieve platelet recovery before the end of the study, the time to platelet recovery will be censored on the last day of the study. CSBE refers to all bleeding events that require intervention including, but not limited to, transfusional support (red blood cells, platelets and other blood products such as fresh frozen plasma or cryoprecipitate). CSBE will include hematuria, gastrointestinal bleed, retroperitoneal bleed, intra-cranial bleed, uncontrolled epistaxis and muscle or soft tissue hematomas.

**2) Kinetics of granulocytic recovery:** Parameters to be assessed will include the median time to reach absolute neutrophil count (ANC) equal to or greater than  $500/\mu\text{L}$  (first of the five consecutive days with ANC  $\geq 500/\mu\text{L}$ ) and the median time to reach ANC equal to or greater than  $1000/\mu\text{L}$  (first of the five consecutive days with ANC  $\geq 1000/\mu\text{L}$ ) counted from the first day of study drug administration. A neutrophil response will be defined as an absolute increase in ANC of more than  $1000/\mu\text{L}$  within 4 weeks of remission IC.

**3) Kinetics of erythrocytic recovery:** Parameters to be assessed will include the median number of days needed to reach a hemoglobin level  $> 8\text{ g/dl}$  (first of the 5 consecutive days with hemoglobin  $> 8\text{ g/dl}$ ) starting from the first day of study drug administration, maximal rise in hemoglobin level after achieving transfusion-independence and rates of red blood cell transfusion-independence within 4 weeks of IC. An erythroid response in patients with a pretreatment hemoglobin level of  $< 8\text{ g/dL}$  (transfusion-dependent) will be defined as an increase in the hemoglobin level by  $1.5\text{ g/dL}$  or more without transfusion of packed red cells that is sustained for at least 2 weeks (from the start date of eltrombopag) or a 50% reduction in the number of units of packed red cells transfused in the 2 consecutive weeks following eltrombopag use compared to the transfusion requirement in the 2 weeks preceding use of the study drug.

**4) Characterization of platelet response to eltrombopag by AML subtype (WHO classification), etiology of AML (*de novo* versus secondary) and cytogenetic risk groups.**

**5) Treatment/Disease outcomes:** CR rates, time to attain CR, CRp rates, time to initiation of post-remission therapy, rates of refractory or persistent disease, survival and safety profile.

Safety will be evaluated from the incidence and severity of adverse events based on clinical assessment and laboratory evaluations, determined according to the Common Terminology Criteria for Adverse Events (CTCAE), version 4.0 of the National Cancer Institute (NCI) Cancer Therapy Evaluation Program (CTEP). Survival will be calculated from the day of study enrollment until the last follow-up or death. Disease-free survival will be calculated from the date of complete remission until relapse, the date of last follow-up, or death.

Response criteria of AML patients to IC will be based on AML International Working Group (IWG) criteria (**Appendix III**). Modified AML response criteria include: morphologic leukemia free state, morphologic CR, cytogenetic CR, molecular CR and CRp. IWG criteria do not require presence of bone marrow cellularity (usually profoundly hypocellular from the effects of cytotoxic chemotherapy) or absence of dysplasia as a criterion for remission status.

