### **1.3 Thrombocytopenia**

Thrombocytopenia is a common problem in patients with acute leukemia and other hematologic malignancies treated with intensive chemotherapy. The current standard treatment strategy to prevent or manage thrombocytopenia-associated bleeding complications relies exclusively on supportive platelet transfusions. However, this therapeutic approach is expensive, time consuming and associated with risks of alloimmunization and bloodstream infections. Moreover, the effects of platelet transfusions last only for 3-7 days.(17) The incidence of alloimmunization to platelets range from 9-50 % (18,19) and in these patients, platelet transfusions are ineffective in raising platelet counts. Although use of leukoreduced products has reduced the risk of alloimmunization, it still remains at about 4 %. (18) Other immune-mediated problems include febrile reactions and transfusion-related acute lung injury (TRALI). The reported incidence of febrile reaction ranges from 0.13 to 37.5 % per unit in hematology/oncology patients.(20) The incidence of TRALI in patients receiving high-volume plasma products including apheresed platelets has been reported to range from 1 in 1,300 to 1 in 5,000 transfusions.(21-23) In addition, there remains a risk of infections from platelet transfusions. Estimated residual risk of acquiring Hepatitis C Virus (HCV) and Human Immunodeficiency Virus (HIV) from donations from repeat donors (after nucleic acid testing) is 1 per 1,935,000 and 1 per 2,135,000, respectively.(24) The chance of acquiring Hepatitis B virus infection is approximately 1 in 200,000. The risk of bacterial transmission is approximately 1 in 50,000 apheresis platelets.(25, 26)

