### 7.3 Dose Adjustments for Eltrombopag

If after 2 weeks, the platelet count fails to reach 50,000/ $\mu$  L or above, the dose will be increased to 300 mg orally daily (150 mg orally daily for East-Asians). Depending on tolerability, dose modification will be individualized based on the patient's platelet count response according to the following rules:

Dose Modification / Adjustment of Eltrombopag	
If platelet count is $\leq$ 50,000/ $\mu$ L after 2 weeks of treatment with starting dose of eltrombopag*	Increase daily dose to 150 mg for East-Asians and 300 mg for all other ethnicities
If platelet counts are between 50,000 and $<$ 100,000/ $\mu$ L (untransfused) on the starting or escalated dose of eltrombopag	Continue on the same dose
If platelet counts reach $\geq$ 100,000/ $\mu$ L (untransfused) on the starting or escalated dose of eltrombopag at any time on study	Discontinue eltrombopag

\* Starting dose will be 100 mg for East-Asians and 200 mg for other ethnicities.

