## 8.2 Monitoring while taking eltrombopag

The following procedures will be conducted:

- 1) Daily vital signs and physical exam while inpatient and once weekly as outpatient only in those patients still receiving eltrombopag.
- 2) Adverse event (AE) monitoring and documentation will begin starting from the date of study drug initiation. Any AE resulting during or following remission IC but preceding study drug initiation will not be attributable to the study drug. AE's will be recorded as definite, probable, possible, unlikely or unrelated by the treating team in the daily clinical progress note and abstracted for study documentation by approved study personnel (physicians, research nurses and study coordinators).
- 3) CBC with differential will be monitored daily during hospital stay. Once the patient is discharged, CBC with differential will be checked within 72 hours, thereafter CBC with differential will be checked weekly until the subject's platelets reach 100,000/ $\mu$ L.
- 4) Complete metabolic panel (CMP) will be checked daily during hospital stay. Once the patient is discharged, CMP will be checked weekly until the subject's platelets reach 100,000/ $\mu$ L.
- 5) Documentation of all infections requiring treatment with intravenous antimicrobials (antibacterial, antiviral or antifungal) by date (the period to be covered for documentation purposes starts at day 1 of study drug administration).
- 6) Concurrent medication review (with each clinical assessment) for the entire period on the study drug.
- 7) Documentation of all red blood cell and platelet transfusions including dates of transfusion while on eltrombopag.
- 8) 12 lead electrocardiograms pre- and post-dose on the first day of eltrombopag administration and thereafter only if clinically indicated. The post-dose ECG is to be performed within a 2-4 hour window post-dose (preferably within 3 hours after administration of study medication). If assessment cannot be performed at 3 hours post-dose, record actual time of ECG performed.

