### 10.1.2 Response to Eltrombopag

**Complete Response to eltrombopag** will be defined as improvement in platelet count (independent of platelet transfusions) to  $\geq 100,000/\mu\text{L}$  with eltrombopag that lasts for at least 4 weeks after discontinuation of eltrombopag. The date of achieving complete response to eltrombopag was defined as the first day of the four-week period with platelet count greater than  $100,000/\mu\text{L}$  off eltrombopag and independent of platelet transfusions. If the patient with platelet counts  $\geq 100,000/\mu\text{L}$  transition to subsequent post-remission therapy within the 4-week timeframe of eltrombopag discontinuation, then that will be considered a complete response.

**Partial Response to eltrombopag** will be defined as any improvement in platelet count to  $\geq 50,000/\mu\text{L}$  but less than  $100,000/\mu\text{L}$  despite use of the highest dose of eltrombopag for the entire duration of the study or drop in platelet counts to  $< 100,000$  after achieving complete response (necessitating resumption of eltrombopag treatment).

**No response (NR) is defined as failure to fulfill the above criteria for either complete response or partial response after 8 weeks of eltrombopag therapy and despite use of maximal escalated dose of eltrombopag.**

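### Section 10.2(1): the five-day platelet recovery run may begin the day after a platelet transfusion, so transfusion-independent recovery can be dated up to 3-7 days early

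*Combined protocol and SAP*

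**What the plan says.** Section 10.2(1) lists the platelet recovery parameters, among them the time to transfusion-independent recovery and the rate of transfusion independence. On the origin it says "The initial time point for assessing different platelet recovery periods will be the first day of remission IC". The event date runs "until the first of the 5 consecutive days with platelet count equal to or greater than" 50,000/µL. The transfusion condition and the words that follow it are "without a platelet transfusion. For patients who do not achieve platelet recovery before the end of the study": the text goes straight on to censoring and sets no transfusion-free interval before the run. The rate of transfusion independence is listed there but not defined.

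Section 1.3, in the background on thrombocytopenia, says that "the effects of platelet transfusions last only for 3-7 days".

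No other section fills the gap. The dose-adjustment table in 7.3 refers to untransfused counts without an interval. Section 10.1.2 defines complete response as "improvement in platelet count (independent of platelet transfusions) to" 100,000/µL or more, also without an interval. Section 12 does not address the matter.

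On data collection, Section 8.2 provides for "Documentation of all red blood cell and platelet transfusions including dates of transfusion while on eltrombopag" and says "CBC with differential will be monitored daily during hospital stay". The study calendar in 8.4 records transfusion history before induction and in each of weeks 1 to 6.

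**The concern.** This endpoint is meant to show platelet recovery that does not depend on transfusion. Its transfusion condition covers only the five run days, and recovery is dated to the first of them. If the run starts soon after a transfusion, that first day is the one most likely to carry transfused platelets. The recorded date can then reflect when the last transfusion was given rather than when the marrow recovered.

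Any such error makes recovery look earlier, never later. The trial has a single arm, so no concurrent control group carries the same error. Platelet transfusion independence is named in the secondary objectives (2.2) and comes first among the secondary goals in Section 12, so the endpoint is likely to be read as evidence of the drug's effect on platelets.

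The platelet rule is also lighter than its red-cell counterpart. In 10.2(3), the hemoglobin-rise form of erythroid response must hold for at least 2 weeks without red-cell transfusion.

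**Working it through.** **The plan's own figures.** The plan gives no computed figure for this endpoint. Its only design figures belong to the primary endpoint (Section 12): 12 patients in stage 1, continue with 8 or more; 31 in all, accept with 21 or more.

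- Early stop = P(X ≤ 7 | n = 12, p) = 56.2% at p = 0.60 and 7.3% at p = 0.80.
- Overall rejection = 1 − Σ(x = 8 to 12) P(X₁ = x | 12, p) · P(X₂ ≥ 21 − x | 19, p) = 80.6% at 0.60 and 8.9% at 0.80.

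These agree with the stated 56%, 7%, 81% and 9% after rounding. They do not use the five-day run, so nothing below changes them.

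**Inputs for this point.**
- Run length: 5 days, dated to the first (10.2(1)).
- Transfusion-free days required before the run: none (10.2(1)).
- Duration of transfusion effect: L = 3 to 7 days (1.3).

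**Day counting under the rule as written.** Put the last transfusion on day 0. The earliest run then occupies days 1 to 5. Take an effect of L days to cover days 1 to L.

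- Run days inside the effect = min(5, L).
- First day free of the effect = L + 1.
- Possible backdating = (L + 1) − 1 = L days, if native counts hold at 50,000/µL from day L + 1.

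| Effect L (days) | Run days inside the effect | Native run days | First effect-free day | Possible backdating (days) |
|---|---|---|---|---|
| 3 | 3 of 5 | 2 | 4 | 3 |
| 4 | 4 of 5 | 1 | 5 | 4 |
| 5 | 5 of 5 | 0 | 6 | 5 |
| 6 | 5 of 5 | 0 | 7 | 6 |
| 7 | 5 of 5 | 0 | 8 | 7 |

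For L = 3 or 4 the run must end on native counts at or above the threshold, so the recovery is real and only its date is in doubt. For L = 5 to 7 no run day need be native, so the recovery itself may not have happened. Five days is shorter than the upper end of the 3-7 day range, so the run alone cannot exclude transfused platelets.

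**Day counting with a look-back of w transfusion-free days.** The earliest first day becomes w + 1 and the earliest last day w + 5.

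- w = 3: run on days 4 to 8. Its last day falls after day 7, so even a 7-day effect leaves one native run day. Remaining backdating is at most L − 3, that is 0 to 4 days.
- w = 7: run on days 8 to 12. No run day lies inside a 7-day effect, so there is no backdating within the protocol's range. A patient whose native counts had already recovered is dated late.

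The two look-backs therefore bracket the date from the early and the late side.

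**The case against.** Section 1.3 is a background remark on the limits of transfusion. It does not say that one transfusion keeps the count at or above 50,000/µL for 3-7 days. Some remaining effect is not the same as meeting the threshold because of it, and the run demands that level on five consecutive days with no further transfusion. Transfusion practice is left to the institution (4.1, 5.10.6), so it cannot be judged how far a transfusion would carry a patient. The endpoint is secondary, has no benchmark or decision rule, and Section 12 describes these goals as estimation. A 7-day look-back used alone would bring the opposite error.

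Much of this stands. It limits the point to what the rule permits, and it is why a 7-day look-back should not be the only version. It does not remove the gap: the rule can still be followed exactly and give a wrong date.

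Four stronger readings are tempting and are not supported:

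- A reader might infer that recovery is in general dated too early. The documents give no frequency of runs that start within 3-7 days of a transfusion.
- A reader might turn the shift into percentage points recovered by a given day, using the historical median of 24 days (range 17-57) in 10.1.1. That figure is stated without a transfusion condition or a five-day run. The calculation would also need an assumed curve and an assumed share of patients affected.
- A reader might infer that a patient transfused the day after the run is counted as transfusion-independent in the rate. The rate is undefined, so this holds only if it borrows the same rule.
- A reader might infer that the efficacy decision is biased toward the drug. That decision rests on the primary endpoint, which does not use this run.

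**Conclusion.** The point holds as a defect in a stated rule. As written, 10.2(1) can date transfusion-independent recovery up to 3 days early with a 3-day transfusion effect and up to 7 days early with a 7-day effect. With an effect of 5-7 days it can also accept a run made up wholly of transfusion-supported days.

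This rests on three conditions: the 3-7 day figure in 1.3 applies to these patients, the run starts inside that window, and the transfusion is what lifts the early counts to 50,000/µL. How often all three hold, and so the effect on the median, cannot be computed from the documents. The primary endpoint, the sample size and the cut-offs of 8 of 12 and 21 of 31 are unaffected. The change is still worth making, because the error runs in one direction, the trial has no concurrent control, and the data needed are already collected.

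**What to change.** In 10.2(1), add that no platelet transfusion may have been given in a stated number of days before the first day of the five-day run. Report the endpoint twice, with a 3-day and with a 7-day look-back, and present the two as a range for the recovery date. State whether the transfusion-independence rate uses this definition; if it does, apply the same look-back there. Score any historical comparison by the same rule.

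The cost is analysis wording. Transfusion dates are recorded during treatment (8.2) and across weeks 1 to 6 (8.4), so days before the first dose are covered as well. No visits, patients or changes in transfusion practice are needed.

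The downside is that some recovery dates move later, and the 7-day version may date some true recoveries late. A later run is also more likely to fall after discharge, when 8.2 calls for a count within 72 hours and then weekly, so the wording should say how a five-day run is scored from outpatient counts.

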#### 6.4 Bleeding Following Discontinuation of eltrombopag

Following discontinuation of eltrombopag, platelet counts return to baseline levels within 2 weeks in the majority of patients, which increases the bleeding risk and in some cases may lead to bleeding. Assessment of bleeding will be performed throughout the study from screening until the last dose of study drug or patient withdrawal from the study. Bleeding will be assessed by the WHO Bleeding Scale (Appendix V: WHO Bleeding Scale). Platelet counts will be monitored as part of daily CBC measurements during the period of hospitalization and thereafter once weekly as outpatient following discharge for 4 weeks following discontinuation of eltrombopag.

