d. **Transfusion History:** Transfusion requirements of red blood cells and platelets up to 8 weeks prior to the diagnosis of AML and during hospital stay.

e. **Physical Examination:** Weight, height (during screening only), body temperature (oral), blood pressure, pulse rate, respiratory rate and pulse oximetry (oxygen saturation).

f. **CSBE:** Clinically Significant Bleeding Events includes hematuria, gastrointestinal bleed, retroperitoneal bleeding, intra-cranial bleed, epistaxis not controlled by conservative measures and muscle or soft tissue hematomas. CSBE will not include petechial skin rash, ecchymosis or mucosal petechiae.

g. **Performance Status** as per ECOG scale.

h. **Hematology:** CBC with differential will be monitored daily during hospital stay. Once the patient is discharged, CBC with differential will be checked within 72 hours, thereafter CBC with differential will be checked weekly until the subject's platelets reach 100,000/ $\mu$ L. Once the platelet counts reach 100,000/ $\mu$ L, the labs will be done at the discretion of treating physician as part of routine standard of care.

i. **Serum Biochemistry:** Complete metabolic panel (CMP) will be checked daily during hospital stay. CMP will include albumin, total protein, alkaline phosphatase, total bilirubin, SGOT[AST], SGPT[ALT], sodium, potassium, chloride, bicarbonate, BUN, creatinine, glucose, and calcium. Magnesium and phosphorus will be resulted if clinically indicated. Once the patient is discharged, CMP will be checked weekly until the subject's platelets reach 100,000/ $\mu$ L. Once the platelet counts reach 100,000/ $\mu$ L, the labs will be done at the discretion of treating physician as part of routine standard of care. ELISA for HIV and remote hepatitis panel will be checked only once at the time of study screening (pre-induction).

j. **Peripheral Blood Smear:** Will be performed prior to start of induction chemotherapy, typically between day 30 and 45 of induction chemotherapy while checking for remission status, and at the end of the study period (optional) based on clinical assessment.

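### Recovery dates in three blood lineages rest on five-day runs that the post-discharge count schedule cannot show, and no rule covers days without a count

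*Combined protocol and SAP*

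**What the plan says.** Section 10.2 of the combined protocol and SAP measures time to transfusion-independent platelet recovery from the first day of induction "until the first of the 5 consecutive days with platelet count equal to or greater than" 50,000/µL, with no platelet transfusion. Patients without platelet recovery by the end of the study are censored on its last day. Neutrophil recovery, at 500 and at 1000/µL, is dated to the "first of the five consecutive days with ANC" at or above the level. Hemoglobin recovery is dated to the "first of the 5 consecutive days with hemoglobin" above 8 g/dL. The neutrophil and hemoglobin clocks start at the first dose of study drug.

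On the supply of counts, Section 8.2 item 3 says "CBC with differential will be monitored daily during hospital stay". After discharge, "CBC with differential will be checked within 72 hours, thereafter CBC with differential will be checked weekly until the subject's platelets reach" a level of 100,000/µL. Note h to the study calendar (Section 8.4) adds that from then on "the labs will be done at the discretion of treating physician as part of routine standard of care". Section 6.4, on bleeding after the drug is stopped, says "Platelet counts will be monitored as part of daily CBC measurements during the period of hospitalization and thereafter once weekly as outpatient following discharge"; it sets this over the 4 weeks after the drug is discontinued. Section 8.2 item 9 has blood counts collected per standard of care for up to 4 weeks after stopping, or until post-remission therapy if that comes first.

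No section says how to treat a day on which no count was taken.

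**The concern.** The endpoint is defined on a daily grid, and the data leave that grid at discharge. Patients plausibly go home because their counts are recovering, so the unmeasured days are unlikely to fall at random.

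Read strictly, a patient at home with sustained untransfused platelets never completes a run and is censored. Read loosely, the analyst must decide after the fact what confirms recovery and which date it gets. Section 12.0 summarizes platelet and neutrophil recovery by Kaplan-Meier, so event status and date are the whole result. Section 4.1 describes a single-arm trial, so no concurrent control shares the same discharge effect.

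Neutrophils and hemoglobin have a further weakness: the fixed weekly blood count ends on a platelet trigger, whether or not those lineages have recovered.

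**Working it through.** **The plan's own calculation.** Section 12.0 sets 8 of 12 to continue and 21 of 31 to accept, for 60% against 80%. The chance of stopping early is P(X ≤ 7) with X ~ Bin(12, p): 56.2% at p = 0.6 and 7.3% at p = 0.8. The overall chance of rejection is 1 − Σ(x = 8 to 12) P(X = x)·P(Bin(19, p) ≥ 21 − x): 80.6% and 8.9%. These match the stated 56, 7, 81 and 9% to rounding. The inputs are platelets of at least 50,000/µL by day 24, with no stated five-day run, so this calculation is not touched.

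**What the schedule can show.** Let D be the discharge day. Counts exist on every day to D, on one of D+1, D+2 or D+3, and then every 7 days. Require a measured count on each of five consecutive days:

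| Run starts | Days needed | Shown by scheduled counts? |
|---|---|---|
| D−4 or earlier | ends by D | yes |
| D−3 | to D+1 | only if the 72-hour count falls on D+1 |
| D−2 | to D+2 | no: D+1 and D+2 are both needed and only one post-discharge count falls in that window |
| D−1 or later | to D+3 or beyond | no |

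If bracketing counts are accepted instead, the status can be recovered but the date slips: the first scheduled count after a post-discharge recovery comes up to 6 days late.

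**Size, under an assumed model.** Section 10.1.1 gives a historical median of 24 days to platelets above 50,000/µL, range 17–57. A shifted log-normal, 16 + LN(median 8, sigma 0.65), has median 24.0 and 0.5–99.5% points of 17.5 and 58.7. Then F(t) = Φ(ln((t − 16)/8)/0.65). The gap is F(D) − F(D−4), or F(D) − F(D−3) if every patient has a next-day count.

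| Assumed D | F(D) | F(D−4) | Gap | F(D−3) | Gap with next-day count |
|---|---|---|---|---|---|
| 24 | Φ(0) = 50.0% | Φ(−1.066) = 14.3% | 35.7 | Φ(−0.723) = 23.5% | 26.5 |
| 28 | Φ(0.624) = 73.4% | Φ(0) = 50.0% | 23.4 | Φ(0.181) = 57.2% | 16.2 |
| 32 | Φ(1.066) = 85.7% | Φ(0.624) = 73.4% | 12.3 | Φ(0.747) = 77.2% | 8.4 |

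Gaps are percentage points of all patients, taken from unrounded values. Later discharge shrinks the first gap to about 8 points at day 35 and 3 at day 40. Patients who recover after discharge are not in the gap, although they too cannot meet the strict rule from scheduled counts.

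**Cross-check without the log-normal.** With discharge on day 28, a complete inpatient run must start by day 24. At the Section 12.0 rates, patients not recovered by day 24 number 31 × 0.40 = 12.4 at 60% and 31 × 0.20 = 6.2 at 80%. So roughly 12 or 6 of 31 would have no complete inpatient run. This count includes any who never recover.

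**The case against.** The strongest reply is that the text asks for consecutive days, not for five measured counts. An analyst could accept two weekly counts above the threshold with no transfusion between them. That is correct. A reader might infer that patients who recover near or after discharge can never meet the definition, and the documents do not support that: they are silent on bracketing, not opposed to it, and unscheduled counts or a readmission could fill the gap. What remains is that the plan does not state the bracketing rule, so both event status and date are left open.

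A reader might also infer that recovery rates are understated across the board. The five-day wording dates times to recovery. The rates of platelet and red-cell transfusion independence, and the median times to 50,000 and 100,000/µL, carry no stated five-day condition, and the censoring sentence names platelet recovery only.

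The size can fairly be challenged. The discharge days are assumed. One day is applied to everyone, although discharge probably follows recovery. The model has 50% recovered by day 24, where Section 12.0 plans on about 60%. It covers platelets only. The study calendar seems to place the move to outpatient care around week 5, which would make day 24 an extreme case and leave 12 to 23 points, but the table layout is too uncertain to rely on.

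Finally, scheduled counts do not simply stop at 100,000/µL: Section 6.4 promises weekly platelet counts for 4 weeks after the drug is stopped. That helps platelets. It gives no assurance for neutrophils or hemoglobin.

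**Conclusion.** The point holds in a limited form. The five-day definitions cannot be established from the scheduled outpatient counts, and the plan gives no rule for unmeasured days. If each day needs a measured count, platelet runs starting at D−2 or later are censored as unrecovered, runs at D−3 depend on a next-day count, and times to recovery in all three lineages depend partly on discharge date.

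The indicative size is 36, 23 and 12 percentage points of all patients for discharge on days 24, 28 and 32, or about 27, 16 and 8 if everyone has a next-day count. These figures rest on the fitted platelet distribution, a common discharge day and sustained recovery. They are not shares of the patients who recover, and no neutrophil or hemoglobin data support carrying them over to those lineages.

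Nothing here bears on the primary endpoint or on the decision to accept the drug for further testing. The plan should be changed because the secondary recovery curves cannot otherwise be reproduced from the written definitions.

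**What to change.** In Section 10.2, for platelets, neutrophils and hemoglobin alike:

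- Keep five consecutive days while counts are daily.
- Once counts are not daily, define recovery as a qualifying count confirmed by the next available count at least 5 days later, with no relevant transfusion and no below-threshold count between. Date it to the first of the two.
- State how a qualifying last available count with no later count is classified, for example after platelets reach 100,000/µL or when post-remission therapy begins. The rule must not assume that a further blood count exists after 100,000/µL.
- Add a sensitivity analysis that treats post-discharge recovery dates as interval-censored, between the last non-qualifying and the first qualifying count.

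The change is to wording and analysis. It adds no visits and uses counts largely collected already; transfusions are documented on treatment and in short-term follow-up (Sections 8.2 and 8.3). The cost is precision: outpatient dates may be late by up to about a week, and some fast recoverers may still rest on the stated convention for an unconfirmed last count.
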